For the CC/Stepped Care arm, exploratory analysis will be conducted to determine which parts of the intervention, e.g., number of CM and CHW contacts, were more successful in improving BP control and reducing systolic BP, or if there was an overall “dose” effect.

Power calculation

We aim to recruit a total of $n=1,890$ unique patients. We planned for 20% random attrition which would yield an analytic sample of 1,500 (effective size of 50 patients per practice).^{104,105} A review of cluster-randomized trials in primary care found a median intracluster correlation coefficient (ICC) of 0.04, with an interquartile range of -0.02 to 0.21.¹⁶⁴ Assuming a 5% ICC, 15 clusters of 50 patients per intervention arm and a two-sided alpha of 0.05, we will have 80% power to detect a difference in proportion of patients with BP controlled of 11-13% (depending on whether the proportion controlled in the SCP arm is 50%-70%). With the same assumptions and sample size, using a two-sample t-test, we will be able to detect an effect size of 0.278. Operationalizing this for the primary and important secondary outcomes, we anticipate that for PAM-13, estimating a $SD=10.0$,¹⁶⁵ we would be able to detect a mean difference of 2.78 between the CC/Stepped Care and SCP arms; for systolic BP, estimating a $SD=19.5$ mm Hg,¹⁵³ we could detect a mean difference of 5.42 mm Hg between the CC/Stepped Care and SCP arms.

Design Considerations:

Participants will be considered to be enrolled at the time they are given their randomization assignment, which will occur at the end of the baseline interview. Data from all enrolled participants will be analyzed as intent-to-treat.

Missing Data

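### The power paragraph uses two different reference distributions: on the basis that gives its 0.278, the detectable difference in BP control is about 12-14 points, not 11-13

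*Combined protocol and SAP*

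**What the plan says.** The Power calculation in Section 8 (Analysis) first reduces the recruitment target of 1,890 for loss to follow-up: "We planned for 20% random attrition which would yield an analytic sample of 1,500", that is, 50 per practice. It then sets the design inputs, "Assuming a 5% ICC, 15 clusters of 50 patients per intervention arm", with a two-sided alpha of 0.05.

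Two detectable effects follow:

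- Binary primary outcome (BP control at 12 months): 80% power is claimed for a "difference in proportion of patients with BP controlled of 11-13" percentage points, "depending on whether the proportion controlled in the SCP arm is 50%-70" percent. No test or reference distribution is named.
- Continuous outcomes: "With the same assumptions and sample size, using a two-sample t-test, we will be able to detect an effect size of 0.278". The paragraph converts this to 2.78 PAM-13 points (SD 10.0) and 5.42 mm Hg systolic (SD 19.5). No degrees of freedom are given.

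The planned analysis of BP control, under the plan for primary outcomes in the same section, is GEE with a logit link and robust standard errors. No small-sample or degrees-of-freedom correction is mentioned.

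**The concern.** The paragraph presents the two effects as coming from one set of assumptions, so a reader expects both to follow from the same ICC, cluster numbers and reference distribution. They do not. The continuous outcomes appear to carry the penalty for having only 30 randomized units; BP control does not. The primary clinical outcome is thus sized on the more favourable basis.

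What is at stake is how far the quoted detectable difference can be trusted. The protocol itself calls 30 practices a relatively small number of clusters (Section 4, D), and it replaced two lost practices partly so as not to be underpowered at 28. Readers will use the quoted range to judge which effects the trial could reasonably have found.

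**Working it through.** **Inputs (all from the Power calculation).** 15 practices of 50 per arm; ICC 0.05; two-sided alpha 0.05; power 80%; SCP control rate 50% to 70%.

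**Effective sample size.**
- Design effect = 1 + (50 − 1) × 0.05 = 3.45.
- Effective n per arm = 15 × 50 / 3.45 = 750 / 3.45 = 217.4.

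**Reproducing the 0.278.** The standard error of a standardized difference is √(2/217.4) = 0.0959.

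| Reference | Detectable effect at 80% power |
|---|---|
| Normal: (1.960 + 0.842) × 0.0959 | 0.2687 |
| t, 1,498 df (patients) | 0.2689 |
| t, about 433 df (effective patients) | 0.2693 |
| t, 28 df (practices: 2 × (15 − 1)) | 0.2784 |

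The noncentral t was used for the t rows. For 28 df, the shortcut (2.048 + 0.855) × 0.0959 gives 0.2785. Only 28 df rounds to 0.278.

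**Reproducing the 11-13 range.** The detectable difference d solves d = 2.802 × √{[p(1 − p) + (p + d)(1 − p − d)] / 217.4}, with p the SCP rate.
- SCP 50%: d = 13.2 points (13.3 with pooled null variance).
- SCP 70%: d = 11.4 points (11.5 pooled, 11.49 before rounding).

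To the nearest whole point these are 13 and 11, so the stated range reproduces with a normal reference.

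**The same calculation on 28 df (noncentral t, unpooled variance).**
- SCP 50%: 13.7 points.
- SCP 70%: 11.8 points.

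Pooled or arcsine variance gives 13.7-13.8 and 11.8-11.9. On the logit scale, power at 14 and 12 points is 80.9% and 80.1%. All variants support 12-14 in whole points.

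**Power at the quoted differences, and where the shortfall arises.**

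| | SCP 50%, +13 points | SCP 70%, +11 points |
|---|---|---|
| Standard error, unpooled | 0.0471 | 0.0409 |
| Difference / standard error | 2.758 | 2.689 |
| Power claimed | 80% | 80% |
| Normal reference, exact whole-point difference | 78.7% | 76.7% |
| t, 28 df, exact whole-point difference | 75.9% | 73.7% |
| Lost to whole-point rounding | 1.3 | 3.3 |
| Lost to the reference distribution | 2.8 | 3.0 |

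At the unrounded normal-theory differences (13.2 and 11.4 points), moving to 28 df lowers power from 80% to about 77% in both cases. The detectable difference itself moves by 13.7 − 13.2 = 0.5 point and 11.8 − 11.4 = 0.4 point.

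**The case against.** The strongest reply is that nothing has been miscalculated. Figures of 13.2 and 11.4 become 13 and 11 by ordinary rounding, using a standard method for two proportions. The shared assumptions can be read as the ICC, cluster numbers and alpha only; the t-test is named for the continuous outcomes, and 28 df appears nowhere. A normal reference also matches the GEE as written, which has no degrees-of-freedom correction.

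Much of this stands. A reader might infer that the sum failed, that the figures were rounded down, or that the whole drop from 80% to 74-76% is due to the reference distribution. The documents support none of these: the range reproduces, the rounding is ordinary, and part of the drop is display rounding.

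The point survives because both figures are offered for the same 30 randomized practices. If 28 df is appropriate for the continuous outcomes, the binary outcome has no more independent units. The absence of a correction in the GEE plan does not supply any. Nor does the normal reference rescue the quoted power at exactly 13 and 11 points, where it gives 78.7% and 76.7%.

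A second reply is that the ICC matters more. At 0.04, the median from the review the plan cites, t on 28 df gives 12.7 and 11.0 points, so 11-13 would hold. That is correct and keeps the issue in proportion. But the paragraph states 5%, and the quoted range should follow from the stated ICC.

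**Conclusion.** Wrong as written, and modest in size. On the basis that generates 0.278, 80% power corresponds to 13.7 points at an SCP rate of 50% and 11.8 points at 70%. Power at the quoted 13 and 11 points is about 76% and 74%, with roughly 3 points of each shortfall due to the reference distribution and the remainder to whole-point rounding.

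This rests on the plan's ICC of 0.05, equal clusters of 50, no gain from covariate adjustment, and 28 df, which is inferred from 0.278. It does not show that the trial is underpowered in any material sense, and a null result should in any case be read from its confidence interval.

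**What to change.** Restate the BP-control line as 80% power to detect a difference of about 12-14 percentage points (11.8 at an SCP rate of 70%, 13.7 at 50%). State that t on 28 df (30 practices minus 2) is the reference for both the binary and the continuous figures. Giving one decimal removes the rounding component.

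The cost is one or two sentences in the Power calculation and a slightly less favourable quoted figure. Sample size, number of practices and conduct are unchanged.

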1. **Step 3 - Telephone Screening and Oral Consent:** After a waiting period of 10 days, patients who have not contacted the study recruitment center to opt out of the study are followed up by telephone. During the phone call, potentially eligible persons are asked if they are interested in participating in the study. We screen persons (both those contacted by us and those who reach out to us in response to the mailing) for eligibility using a set of prepared questions. Eligible patients who remain interested in the study are read the oral consent form. If the patient agrees to participate, the telephone baseline interview is completed. In cases where patient is unable to complete telephone baseline interview due to limited phone minutes, paper version of the baseline interview will be mailed to the patient with returned envelope. When the baseline data collection has been completed, patients are informed of the assignment group of their practice. If the recruitment goal has not been reached within a reasonable amount of time, we mail another batch of letters and repeat this process until the recruitment goal of an average of 63 participants per practice is met, or recruitment closes at the practice.
2. **A participant is considered enrolled in the study once they have completed the baseline survey.** In order for a participant to successfully complete the baseline survey they must complete the PAM, PHQ, PROMIS Global scale, adverse events questions, and demographics questions. The eligibility BP measurement will be the participant's baseline BP measurement in both arms. Consented participants in both arms will continue to attend their typical schedule of primary care appointments. We do not require a specific frequency of primary care visits during the study period.
3. **Step 4 – First Intervention Visit for Patients in CC/Stepped Care Practices Only:** The First Intervention Visit is conducted by the Care Manager (CM) at the participant's primary care practice. The participant is invited to meet both the CM and CHW. BP, height and weight measurements will be taken by typical personnel and in a manner that follows the practice site's normal procedures. The participant receives and is trained on the use of the home blood pressure monitor.

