For the Patient Survey (telephone interview) data: To limit missing data at baseline, we are not considering the patient to be enrolled in the study until they complete the baseline survey. We make the participant fully aware of the time involved to complete the survey prior to beginning. We also give the participant the option to complete the survey in more than one telephone call. Our interviewers are trained to encourage the participant to complete the entire survey. Though the participant may choose not to answer some of the questions, we are requiring that they answer at least 10 items of the PAM-13 since this is a primary outcome. Participant data entered into REDCap will be reviewed weekly by the data manager for completeness. If data were inadvertently missing (the participant did not refuse to answer), the interviewer will be asked to re-contact the participant to obtain these data. If there are patterns of missing data across interviewers, we will work to identify why this is occurring and modify training, as necessary, to correct the issue. We are using the scheduling system within REDCap to track when participants are due for follow-up telephone surveys. Additionally, if patients are still being seen at the participating health system, we will have access to updated telephone numbers and addresses. We have tried to minimize study participant burden and follow-up interviews should take less time to complete than the baseline. We will seek to replace dropout patients with others from the same clinic when these occur early in the intervention period. A dropout is defined as any participant who, after completing the baseline survey and receiving their randomization assignment, states that s/he wants to withdraw from the study and receive no further contact from the study team. If this occurs within two (2) months of the date of randomization, we will attempt to recruit an additional patient from the same practice.

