4. *Randomized trial:* The human subjects in this phase of the proposed research are 1,890 patients with hypertension (HTN) and associated comorbidities who receive their primary healthcare at partnering health systems, as well as the clinicians and staff of each practice and leadership of the systems to which the practices belong. The research will include an average of 63 patients at each of the 30 participating practices within these health systems. As our study design is a cluster randomization of practice sites, not participants, patients will be assigned to the study condition, SCP or CC/Stepped Care intervention arm, of the practice they attend for healthcare. Patients are surveyed prior to learning the random assignment of their practice and are given information on each condition and asked if they are willing to participate, given that they may end up in either condition. Clinicians and staff will be asked their opinions about their workplace and their satisfaction with the program. Leaders will be asked about the capacity and priorities of their systems.

b. **Adequacy of Protection Against Risks and Potential Benefits**

- i. **Education in protection of human research participants:** Education in the protection of human research participants and good clinical practice has been met by certified completion of the Johns Hopkins University School of Medicine or School of Public Health Web-based Research Compliance course, “Human Subjects Research Training” by all relevant Key Personnel. The course consists of the University of Minnesota Web modules on Informed Consent, the Consent Process, and After Informed Consent, a Johns Hopkins University School of Medicine module on local IRB requirements, and achievement of a passing score on the Johns Hopkins Knowledge Assessment module. Training in the Health Insurance Portability and Accountability Act (HIPAA) has also been met by certified completion of the Johns Hopkins University School of Medicine’s Web-based HIPAA training course.
- ii. **Recruitment and Informed Consent:**
 1. *Recruitment for Kick-Off/Town Hall Meetings:* Identified stakeholders in the proposed research are invited to attend town hall meetings by letter/email from the Principal Investigators (PIs). Letters are sent at least two months prior to meetings to allow adequate planning time for stakeholders.

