5. *Patient Recruitment for Trial:* Patients who are age 21 years or older, receiving primary care at one of the 30 participating practices, have a diagnosis of HTN, and a systolic BP of greater than or equal to 140 mm Hg in the past 6 months, will be recruited for participation in the study. Eligible patients will also have at least one additional cardiovascular risk factor including: diagnosis of diabetes mellitus, hyperlipidemia, coronary heart disease, or depression; or current tobacco smoker. Patients meeting the above criteria will be excluded from the study if they meet any of the following exclusion criteria: serious medical condition which either limits life expectancy or requires active management (e.g., certain cancers), condition which interferes with outcome measurement (e.g., diagnosis of end stage renal disease or on dialysis), pregnant or planning a pregnancy during study period, alcohol or substance use disorder if not sober/abstinent for greater than or equal to 30 days, or planning to leave the practice or move out of geographic area within 24 months. Nursing mothers would need approval from a physician. The research team will identify a listing of patients meeting the inclusion and exclusion criteria at each of the practices in the quarter prior to intervention roll-out. We obtained a HIPAA waiver to screen the EMR for potentially eligible patients. We will mail our selected sample of patients a packet that includes a letter from the practice and the study principal investigators advising them that they are eligible to participate in the study, along with a brief brochure with the study eligibility criteria, objectives, what they would be asked to do as a study participant, a copy of the Oral Consent form, and information on how to contact the study recruiters by telephone. Packets will include a self-addressed refusal post card allowing contacted patients to decline participation. If the study coordinating center does not hear from the potential participant within 10 days, trained recruiters will attempt to contact them by telephone to assess their willingness to participate in the study and complete eligibility screening, oral consent, and a baseline telephone questionnaire using a standardized telephone script. Enrolled participants in the CC/Stepped Care intervention arm will then be scheduled for the First Intervention Visit by CMs, to occur within 14 days of recruitment, whenever possible. For the intensive intervention arm providers, the health system, practice, and administrative champions will assist the research manager in the recruitment of practice providers for participation in the quality improvement and disparities in care training and subsequent follow up webinars. The champions and research manager will notify the providers that they may elect to not participate in the training by not attending the training and subsequent webinars. Attendance to the training and webinars will serve as consent for participation in this part of the intervention.

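### Baseline survey items missed by accident can be collected after the patient has been told the arm

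*Combined protocol and SAP*

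**What the plan says.** **The principle.** Risks to Human Subjects (Randomized trial): "Patients are surveyed prior to learning the random assignment of their practice".

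**When the arm is disclosed.** Section 5E, Step 3: "When the baseline data collection has been completed, patients are informed of the assignment group of their practice". Section 8, Design Considerations, is more specific and ties disclosure to the close of the interview: "Participants will be considered to be enrolled at the time they are given their randomization assignment, which will occur at the end of the baseline".

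**How gaps are found and filled.** Section 8, Missing Data, on the patient survey: "Participant data entered into REDCap will be reviewed weekly by the data manager for completeness". Where an item was left out by accident rather than refused, "the interviewer will be asked to re-contact the participant to obtain these data".

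**What must be in place to enroll.** Section 5E, item 2, counts the baseline survey as complete once the PAM, PHQ, PROMIS Global, adverse-event and demographic questions are done. Section 8, Missing Data, sets a floor of 10 of the 13 PAM items. Medication adherence, PACIC-Plus, trust, and hypertension knowledge and attitudes are patient-reported secondary outcomes, but they are not on the required list.

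**When the intervention starts.** Patient Recruitment for Trial, on the First Intervention Visit in CC/Stepped Care: "to occur within 14 days of recruitment, whenever possible". No minimum gap is given.

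**The concern.** PAM-13 is the primary patient-reported outcome. It and the patient-reported secondary outcomes are analysed as change from baseline, so their baseline should be fixed before the patient knows the arm. The stated order is interview, disclosure, weekly check, call-back. An item obtained at the call-back is answered by someone who already knows whether a care manager and a home monitor are coming, and who may already have met the care manager. If that knowledge moves answers differently in the two arms, the difference in change is biased, and a larger sample does not remove the bias. The text does not ask for recovered items to be dated, flagged or kept out of the baseline score, so the breach would leave no record for the analyst.

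**Working it through.** **1. The plan's own yardstick.** Inputs from Power calculation, Section 8: ICC 0.05, 15 clusters of 50 per arm, two-sided alpha 0.05, 80% power, PAM-13 SD 10.0.

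- Design effect = 1 + (50 - 1) x 0.05 = 3.45.
- Effective sample per arm = 15 x 50 / 3.45 = 217.4.
- Detectable effect, t reference with 30 - 2 = 28 df: (t at 0.975 + t at 0.80) x sqrt(2/217.4) = 0.278 SD, or 2.78 PAM-13 points. This matches the plan. The normal approximation gives 0.269.

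The 2.78 points is therefore sound, and it serves below only as a yardstick.

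**2. The order of events.**

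| Event | Timing in the documents | Place |
|---|---|---|
| Baseline interview ends; arm disclosed | Day 0 | Section 8, Design Considerations; Section 5E, Step 3 |
| Completeness review | Weekly, so up to about 7 days later | Section 8, Missing Data |
| Re-contact for accidental gaps | After the review; no deadline | Section 8, Missing Data |
| First Intervention Visit (CC/Stepped Care only) | Target by day 14; no minimum gap | Patient Recruitment for Trial |

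Re-contact normally follows disclosure. It may follow the First Intervention Visit, since nothing requires it to be finished first. No single sentence states this sequence; it follows from reading the sections together.

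**3. What is exposed.**

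- Refused items: no. Re-contact is limited to accidental omissions.
- Blood pressure: no. Section 5E, item 2, takes the eligibility reading as baseline.
- A survey split over several calls and still unfinished: no. The arm has not yet been given.
- PAM-13: at most 3 of 13 items, from the 10-item floor.
- Medication adherence, PACIC-Plus, trust, hypertension knowledge: accidentally missed items, with no stated limit on their number.

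**4. Size for PAM-13.** The planned model contains arm, time and their product, so with complete data the product term is the difference in mean change. A net shift in the CC/Stepped Care baseline mean passes straight into it with the sign reversed:

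absolute bias = f x (3/13) x s

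Here f is the share of CC/Stepped Care patients with recovered items and s is the shift in points if the whole scale were answered after disclosure, net of any shift in SCP. Items are taken to count equally. Neither f nor s is in the documents; both are assumptions.

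| f | s = 1 | s = 5 | s = 10 |
|---|---|---|---|
| 2% | 0.005 | 0.023 | 0.046 |
| 10% | 0.023 | 0.115 | 0.231 |
| 20% | 0.046 | 0.231 | 0.462 |

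A middle case, f = 10% and s = 3 points (0.3 SD), gives 0.10 x 3/13 x 3 = 0.07 point, and 0.07/2.78 = 2.5% of the detectable difference. The top corner is 0.46/2.78 = 17%, and it needs every affected patient to have three accidentally missed PAM items.

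**The case against.** **Section 5E may already protect the baseline.** It ties disclosure to completed baseline data collection, which could be read as after gaps are filled. But Design Considerations ties it to the end of the interview, and Section 5E itself defines completion by five components only. A survey can meet that definition with gaps in other scales. The wording should be reconciled; it does not remove the problem.

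**The 10-item rule is mainly a tolerance for refusals.** This stands. The rule follows directly on the statement that participants may decline questions, and refused items are not chased. A reader might infer that any patient enrolled with 10 PAM items has three recovered later. The text does not support that, so 3/13 is a ceiling.

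**Whole secondary scales are unlikely to be collected late.** This also stands. A reader might infer from the short required list that entire instruments are filled in after disclosure. That would need an interviewer to skip an instrument by accident, while interviewers are trained to press for the full survey and may spread it over several calls. On that reading, 10% of patients shifted by 0.3 SD would give 0.10 x 0.3 = 0.03 SD, about 11% of 0.278. The documents do not support it as an expected size.

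**The review rule is general.** The paragraph covers follow-up surveys too, so the share of re-contact that concerns baseline is unknown. This stands, and it is why no rate is claimed.

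**A manual may settle it.** Section 9 refers to a Manual of Procedures for screening, recruitment and enrollment. It could set the order of the call; the gap shown here is in the protocol and SAP text.

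**Conclusion.** The order of events holds on the documents: the weekly check and call-back come after disclosure, against the plan's own principle, and no rule marks or handles the late items. Practices were randomised earlier, so what matters is when the patient was told.

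The effect is small. On the assumed 2-20% of patients and 1-10 points, PAM-13 bias is about 0.005-0.46 point against a detectable 2.78. Its direction is unknown: if learning of the intervention raises CC/Stepped Care baseline answers, the estimated benefit shrinks; if it lowers them, the benefit grows. SCP patients also learn their arm, so only the net difference counts. Call-back after the First Intervention Visit is a possibility, not something the documents show happening.

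A reader might go further and doubt the primary clinical result or the sample size. Neither follows: BP control and BP change do not use the survey, and the power figure reproduces. The planned baseline tests cover demographic and practice characteristics, so the issue lies in the change scores. This is an inexpensive improvement rather than a threat to the trial's conclusions.

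**What to change.** 1. **Baseline calls still to be made.** Have the interviewer run the REDCap completeness check inside the baseline call, before the assignment is read, and give the assignment only once accidental gaps are filled. Refusals stay as refusals. Align the disclosure wording in Section 5E and Design Considerations with this.
2. **Participants already enrolled.** Flag any baseline item dated after disclosure and report how many there are by arm and scale. Keep the main analysis as planned and add a sensitivity analysis that treats flagged items as missing. Score PAM-13 from the items answered before disclosure where at least 10 were answered, and let the planned mixed model carry other missing baseline scores.

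The cost is a change to the call script and REDCap order, plus a short SAP addition. A few secondary baseline items will be missing in the sensitivity analysis. If enrollment has closed, only the second step applies, and it depends on collection dates being recoverable. No sample-size figure changes.
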